9.3.2 Patient Related Outcome Methods

9.3.2.1 Patient Related Outcome Instruments:

The MDASI-BT will be utilized for this portion of the study. Full instruments are provided in the appendix. In addition, information regarding demographics and treatment history will be collected as part of the larger study and used in this analysis.

The MDASI-BT consists of 23 symptoms rated on an 11-point scale (0 to 10) to indicate the presence and severity of the symptom, with 0 being “not present” and 10 being “as bad as you can imagine.” Each symptom is rated at its worst in the last 24 hours. Symptoms included on the instrument include those commonly associated with cancer therapies, those associated with increased intracranial pressure, and those related to focal deficits. The questionnaires also include ratings of how much symptoms interfered with different aspects of a patient’s life in the last 24 hours. These interference items include: general activity, mood, work (includes both work outside the home and housework), relations with other people, walking, and enjoyment of

life. The interference items are also measured on 0 - 10 scales. The average time to complete these instruments is 5 minutes. The MDASI-BT has been translated into 18 languages [33, 34].

9.3.2.2 Patient Related Outcome Data collection:

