After enrollment on the clinical trial, patients will complete as baseline measures the MDASI-BT. The patient will continue to complete the MDASI-BT at the time of clinical and seizure evaluation as long as the patient remains on the study, unless clinical deterioration makes self-report not possible before that time. The time when patients are unable to complete the self-report questionnaires will be used as part of the study analysis. The MDASI-BT will be completed only by the patient, unless changes in vision or weakness make this difficult. If this occurs, then the caregiver or research assistant may read the questions to the patient or assist with marking the severity number or score as described by the patient. A patient caregiver may complete the questionnaires as a patient-preference proxy if the patient's deficits preclude self-report. These reports will be used for descriptive purposes only. For the telephone interview, the research assistant will read the questions to the patient and mark the response indicated by the patient. If the patient rates any symptom as 7 or higher, the research assistant will instruct the patient to alert his or her physician team and the research assistant will also notify the clinical team that the symptom has been rated as severe by the patient. The forms will be reviewed by the principal investigator or research assistant for completion.

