Received MDASI-BT forms will be checked versus the timing schedule and considered as valid if they fall within 14 days of the scheduled assessment. Compliance rates will be calculated as the number of received valid forms over the number of expected forms. Differences between groups in compliance will be tested by use of Fisher's exact test at every time point. We will use descriptive statistics to describe how patients rate symptom severity and interference with function at each time point. Error bar graphs for each of the symptoms will be constructed at each time point. The proportion of patients rating their symptoms to be 7 or greater (on a 0-10 scale) will also be reported. Differences of at least 2 points will be classified as the minimum clinically meaningful change in the symptom severity and symptom interference measures. For example, an increase of 2 points or more would mean a moderate improvement, whereas a decrease of 2 points or more would be interpreted as moderate worsening. For individual symptoms, a rise in a symptom score means deterioration, whereas a reduced score means improvement of the specific symptom.

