17.3 MD Anderson Symptom Inventory for Brain Tumors (MDASI-BT)

(The MDASI – BT is created by the OMCR programming staff upon request for each protocol. The standard MDASI – BT questionnaire is used as a template. This form will contain coding “landmarks” that enable the data to be scanned into the MDACC data repository for MDASI results. Please contact the OMCR to obtain the questionnaire that is to be attached to the protocol.)

Date: / /
(month) (day) (Year)

Participant's Initials:

PLEASE USE A BLACK INK PEN BTTC 11-01 Patient #:

[figure not shown]
MDASI BT
Protocol Number: BTTC11-01
PI: [name] [name]
Protocol Acc #:

MD. Anderson Symptom Inventory (MDASI - BT)

Part I. How severe are your symptoms?

People with cancer frequently have symptoms that are caused by their disease or by their treatment. We ask to rate how severe the following symptoms have been in the last 24 hours. Please fill in the circle below from 0 (symptom has not been present) to 10 (the symptom was as bad as you can imagine it could be) for each item.

	Not Present	As Bad As You can Imagine									
	0	1	2	3	4	5	6	7	8	9	10
1. Your pain at its WORST?											
2. Your fatigue (tiredness) at its WORST?											
3. Your nausea at its WORST?											
4. Your disturbed sleep at its WORST?											

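### Section 11.3 gives the direction of the 2-point meaningful change on the MDASI-BT backwards

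*Combined protocol and SAP*

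**What the plan says.** Section 11.3 (Patient Reported Outcomes) makes three statements in sequence.

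- The threshold: "Differences of at least 2 points will be classified as the minimum clinically meaningful change in the symptom severity and symptom interference measures".
- The illustration: "For example, an increase of 2 points or more would mean a moderate improvement, whereas a decrease of 2 points or more". The second of these changes, the text goes on, "would be interpreted as moderate worsening".
- The direction for single items: "For individual symptoms, a rise in a symptom score means deterioration, whereas a reduced score means improvement of the specific symptom".

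Section 9.3.2.1 describes the instrument. Severity is rated from 0 to 10, with 0 meaning the symptom is absent. The interference part consists of "ratings of how much symptoms interfered with different aspects" of the patient's life, and "The interference items are also measured on 0 - 10 scales". The form in Appendix 17.3 labels the top of the severity scale "10 (the symptom was as bad as you can imagine it could be" and the top of the interference scale as complete interference.

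**The concern.** The threshold sentence covers severity and interference together, and the illustration follows it without restriction. Read in order, the text says that a patient whose scores go up by 2 has improved, yet on this instrument a higher score is a worse state.

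The direction bears on a question the trial sets itself. Section 1.3 makes evaluation of patient-reported symptoms a secondary objective; Section 1.4 names the MDASI-BT under the exploratory objectives. Section 9.3 asks whether any seizure benefit comes with better symptoms or is offset by worse ones. The second objective in Section 9.3.1 compares the arms on individual severity, mean severity and interference. Section 2.4 names fatigue, drowsiness, and memory and concentration problems as effects of antiepileptic drugs, and each of these is an item on the form. If lacosamide raised such scores by 2 points and the illustration were followed, the rise would be described as an improvement.

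**Working it through.** The plan gives no figure to reproduce here. The check is of scale direction, followed by a count of what the reversal touches.

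**Step 1. Direction of each scale, from the documents.**

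| Measure | Low end | High end | Source | Higher score means |
|---|---|---|---|---|
| Symptom severity | 0, absent | 10, worst imaginable | Section 9.3.2.1; Appendix 17.3, Part I | worse |
| Interference | 0 | 10, complete interference | Section 9.3.2.1 (range); Appendix 17.3, Part II (top label) | worse |
| Alert rule | – | a rating of 7 or more is passed to the clinical team as "the symptom has been rated as severe by the patient" | Section 9.3.2.2 | worse |

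No section describes reverse scoring or a function scale on which a rise would be good.

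**Step 2. The two rules in Section 11.3 against those scales.**

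| Change | Illustration | Sentence on individual symptoms | Implied by the scales |
|---|---|---|---|
| rise of 2 or more | improvement | deterioration | worsening |
| fall of 2 or more | worsening | improvement | improvement |

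The illustration disagrees with the scales in both rows. The sentence on individual symptoms agrees in both.

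**Step 3. Can the two rules apply to different scores?** Suppose the illustration is meant for summary scores and the other sentence for single items. Let every symptom item go from 3 to 5.

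- Each item changes by 5 − 3 = +2, which the second rule calls deterioration.
- Mean severity is the average of those items, so it also changes by exactly +2, which the illustration calls improvement.

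Every component has worsened while their average is said to have improved. The split reading therefore does not make the illustration right for mean severity. It does not help interference either, where higher is also worse and no other sentence in Section 11.3 gives a direction.

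**Step 4. How many score changes are affected.** Take one item scored 0 to 10 at two time points: 11 × 11 = 121 possible pairs. The number of pairs with a rise of exactly k points is 11 − k.

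- Rises of 2 or more: 9 + 8 + 7 + 6 + 5 + 4 + 3 + 2 + 1 = 45.
- Falls of 2 or more, by symmetry: 45.
- No change: 11. One-point change: 2 × 10 = 20. Below threshold: 11 + 20 = 31.
- Check: 45 + 45 + 31 = 121.

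So 45 + 45 = 90 pairs reach the threshold, and the illustration gives all 90 the wrong label.

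**Step 5. How many items are affected.** The form in Appendix 17.3 has symptom items 1 to 22 and interference items 23 to 28.

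- Interference: 28 − 23 + 1 = 6 items, with only the reversed statement.
- Symptoms: 22 items, with two statements that conflict.
- Mean severity: the right direction has to be inferred from the component items.

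Section 9.3.2.1 speaks of 23 symptoms, while the form lists 22. The count here follows the form; the difference does not affect the point.

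**Step 6. What does not change.** The random-effects models are fitted to raw scores and the other descriptive summary is the proportion at 7 or more. Neither uses the 2-point label. Section 11.3 also plans a model for binary symptom measures without defining them. The reversal would enter that estimate only if such a measure were defined by the 2-point rule, and nothing in the text says it will be.

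**The case against.** The strongest reply is that this is a slip in an illustration. The threshold sentence itself carries no direction, the next sentence is right for symptoms, and the form makes the direction of interference plain. No test, responder table or decision rule in Section 11.3 is built on a 2-point change, so no specified estimate or p-value would move. It can also be said that the sentence on individual symptoms is a separate rule, so that the section does not strictly contradict itself. Finally, the 90 of 121 figure follows from any reversed label and says nothing about how many patients would be affected. It also presumes a comparison between two time points, although Section 11.3 names no reference time.

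Much of this stands. The numerical results are safe, the count of score pairs describes reach and not impact, and an attentive analyst would probably notice the error for symptoms. Two things remain. On the separate-rule reading the illustration is still wrong for mean severity and for interference, as Step 3 shows. And for interference the only direction written in the analysis section is the wrong one. A prespecified rule should not depend on the analyst setting it aside, and doing so later without a record would be a departure from the plan.

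**Conclusion.** The concern holds. The direction given for a 2-point change is reversed for the severity and interference measures alike. It conflicts with the plan's own sentence on individual symptoms and stands uncorrected within Section 11.3 for the 6 interference items. Every change that reaches the threshold would carry the wrong label if the illustration were followed.

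The consequence is limited to how 2-point changes are classified and described for a secondary objective. The primary endpoint, sample size, mixed-model coefficients on raw scores and 7-or-more proportion are unaffected. It should be fixed, but it does not threaten the trial's main conclusion.

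The conclusion assumes that the appended form is the one used and that scores are analysed as recorded. The documents give no indication otherwise.

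**What to change.** Replace the illustration in Section 11.3 with: *For all MDASI-BT severity and interference scores, an increase of 2 or more points is worsening and a decrease of 2 or more points is improvement.* This agrees with the existing sentence on individual symptoms and supplies the missing direction for interference and mean severity.

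The cost is one sentence of wording. No data collection, patient burden or sample size is affected.

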7.0 PRETREATMENT EVALUATION

General Requirements

Unless otherwise noted, all pretreatment evaluations must be performed within 14 days prior to the registration. A model study calendar is presented in Figure 8-1.

- 7.1 A complete history and neurological examination (to include demographic information, vital signs, and documentation of the Karnofsky Performance Status per Appendix 17.2) shall be performed on all patients.
- 7.2 Prestudy laboratory tests shall include CBC, differential, platelets, sodium, potassium, bicarbonate, chloride, BUN, serum creatinine, glucose, bilirubin, SGOT, SGPT, alkaline phosphatase, and serum pregnancy test for women of childbearing potential. Patients must agree to practice adequate contraception. The treating physician should use their own discretion regarding how long patient should continue contraception use after discontinuing treatment.
- 7.3 Documentation of tumor diagnosis.
- 7.4 Patients will complete a baseline MDASI-BT (Appendix 17.3) prior to the first dose of study medication at the doctor's office or clinic. At this time the MDASI-BT will be completed only by the patient, unless changes in vision or weakness make this difficult. If this occurs, then the caregiver nurse may read the questions to the patient or assist with marking the severity number or score as described by the patient.
- 7.5 EKG. Required to evaluate PR interval for eligibility.
- 7.6 EEG (optional but should be obtained whenever possible).

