8.0 EVALUATION DURING STUDY

General Requirements

Unless otherwise noted, all evaluations may be performed within 14 days before the scheduled date. A model study calendar is presented in Figure 8-1.

- 8.1 Laboratory tests will be obtained only as deemed necessary by the investigator during study treatment.
- 8.2 All relevant information regarding drugs, doses, laboratory examinations, and treatment-related toxicities shall be documented in the patient's medical record and flow sheets.
- 8.3 A complete history and neurologic exam (to include vital signs and documentation of the patient's Karnofsky Performance Status) will be performed at least every 3 months, +/-2 weeks.
- 8.4 Every 4 weeks when the patient is not seen by the study team, telephone contact between the patient and a study clinician (nurse or MD) is required to assess for possible seizure in the preceding month.. The Site to complete the BTTC 11-01 Interim Telephone Contact Checklistform . Calls or visits must occur on the scheduled date or within 2 weeks prior to the scheduled date.
- 8.5 *EEG should be obtained whenever possible to confirm the clinical impression of seizure.* Because the diagnosis of seizure is frequently made by history, this test is optional.
- 8.6 All patients will be followed for overall survival at least every 3 months, when possible. The follow up will continue until 5 years after the End of Study visit. The follow up can take place via telephone contact by the nurse, study coordinator, or MD.
- 8.7 The MDASI-BT (Appendix 17.3) will be administered every 4 weeks in clinic or by telephone *ONLY* by the nurse or MD.
- 8.8 All patients will be evaluated for adverse events at the monthly telephone calls or visits. In addition all serious adverse events will be reported to the OMCR and the study chair as directed in section 15.7.

Figure 8-1. Model Study Calendar.

	Screening	Start of treatment Visit 1^c (Day 1 of Month 1)	On-treatment period Visits 2-4^c (Day 1 of Months 4, 7, 10)	Last treatment visit Visit 5^c (Day 1 of Month 13)
Demographic data	X			
Drug dispensing/return		X	X	X
Re-Order Drug			X^e	
MDASI-BT ^a		X	X	X
Karnofsky Performance Status	X	X	X	X
EKG ^b	X			
Lab tests ^b	X	X		
EEG ^d	X			
Medical and seizure history	X	X	X	X
Physical and neurologic examination	X	X	X	X
Randomization		X		
Recording of adverse events ^a			X	X
Verification of inclusion/ exclusion criteria	X			
Vital signs	X	X	X	X
Written informed consent	X			

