9.3.1 Patient Related Outcome Objectives

1. To evaluate longitudinal changes in symptom measures and determine the impact of the use of AEDs on these parameters.
2. To measure symptom burden over the course of the study period (one year) evaluate differences between patients individual symptom severity, overall mean symptom severity, and difference in scores on the interference items between those on placebo versus those on lacosamide.
3. To describe the variability of symptom severity longitudinally over the follow-up period.

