Our primary analytic strategy involves the use of a random-effects (or latent growth curve) model to evaluate patient individual and overall longitudinal changes in symptom measures, and determine the impact of the use of AEDs on these parameters. The random-effects model approach provides a generalization to the classic linear regression model. It is ideally suited for analysis of repeated measures data in that it allows for more specific estimation of the correlation structure of the residuals, and more efficiently handles unbalanced designs and is very robust to missing data, without excluding participants or imputing values. In the model, we will include measure time, treatment indicator and their interaction as random effects (i.e., random slopes or latent growth curves). Such a model allows us to evaluate both patient individual and overall longitudinal trajectories of the symptom burden, and also determine the heterogeneity among patient's trajectories (i.e., variance of the random effects). Fit statistics, such as Akaike's Information Criterion (AIC) will be used to select appropriate covariance structure of the dataset. We will use a computer program, PROC MIXED (SAS v9.1 SAS Institute Inc, Cary, NC) to estimate and to test the models with continuous dependent measures. For binary symptom measures, we will use SAS PROC GLMIMX, which provides an adaptation to the mixed model approach for categorical data. To further investigate whether the patient population is consisted of several subpopulations characterized by different longitudinal trajectories. We will also conduct a latent class analysis based on the random-effects model. We allow different latent classes (or subpopulations) have different regression coefficients (i.e., different shapes of growth curves). The AIC will be used to determine the number of latent class and the maximum likelihood method will be used to estimate the unknown model parameters.

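### Section 11.3 names treatment terms for the MDASI-BT model only as random effects, states no fixed effects or treatment contrast, and gives the baseline score no stated role

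*Combined protocol and SAP*

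**What the plan says.** Section 11.3 (Patient Reported Outcomes) plans a random-effects, or latent growth curve, model for the repeated MDASI-BT scores. Its specification is one sentence: "we will include measure time, treatment indicator and their interaction as random effects". The same paragraph gives the aim as to "determine the impact of the use of AEDs on these parameters" and adds: "Such a model allows us to evaluate both patient individual and overall longitudinal trajectories of the symptom burden". AIC selects the covariance structure. There is no list of fixed effects and no named contrast.

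Section 9.3.1 makes the comparison between arms an objective, including the "difference in scores on the interference items between those on placebo versus those on lacosamide". Section 9.3.2 says that "patients will complete as baseline measures the MDASI-BT". Section 7.4 fixes the timing: "Patients will complete a baseline MDASI-BT (Appendix 17.3) prior to the first dose of study medication". Section 8.7 sets the later schedule: "The MDASI-BT (Appendix 17.3) will be administered every 4 weeks in clinic or by telephone". On covariates, Section 9.3.2.1 says that "information regarding demographics and treatment history will be collected as part of the larger study and used in this analysis", without giving these variables a role and without mentioning the baseline score. Section 5.0 stratifies patients for analysis by peri-operative AED use and by institution; Section 11.3 does not take this up.

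**The concern.** Two things are missing from the model statement.

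- **The mean structure.** A random effect describes variation between patients around a mean. A difference between arms is a difference in means and needs a fixed term. A patient belongs to one arm throughout, so a patient-level random treatment effect carries no information that distinguishes it from that patient's random intercept.
- **The baseline score.** It is collected before dosing, but the plan does not say whether it is a covariate, the first repeated response, or unused. Entry is allowed up to 16 weeks after surgery (criterion 4.10) and dexamethasone is permitted (Section 6.1.2), so varied symptom burden at entry is plausible.

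Patient-reported symptoms are a secondary objective, and Section 9.3 wants to know whether worse symptoms offset any seizure benefit. Whoever programs the model from this sentence must supply the fixed effects, the contrast and the baseline handling. Those choices should be made before the data are seen.

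**Working it through.** The documents give no power, SD or correlation for the MDASI-BT analysis, so there is no planned figure to reproduce.

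**Step 1: what the literal model can identify.** Take four random effects per patient: intercept (b0), time (b1), treatment (b2) and time-by-treatment (b3). The sentence does not name the intercept; it is added here as is usual in a growth-curve model. Their covariance matrix has 4 × 5 / 2 = 10 parameters, and the residual variance makes 11. The data show only:

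- placebo arm: the covariance of (b0, b1), 3 quantities;
- lacosamide arm: the covariance of (b0 + b2, b1 + b3), 3 quantities;
- the residual variance, 1 quantity.

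That is 3 + 3 + 1 = 7, so 11 − 7 = 4 parameters are not identified. A numerical rank check over 14 assessments also gave 7. What is identified compares variances between arms, not means.

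**Step 2: what fixed terms add.** One data set was simulated with 302 patients, 14 assessments and a true slope difference of 0.8. With fixed time only (random intercept and time slope), the fit gives an intercept of 2.064 and a time slope of 1.019, and there is no treatment parameter to test. With fixed treatment and treatment-by-time added, the slope difference is estimated at 0.893 (SE 0.193).

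**Step 3: what baseline is worth.** Inputs from the documents are 151 patients per arm (Section 11.1) and assessments every 4 weeks for one year, 52 / 4 = 13 after baseline. All SDs and correlations are assumptions. The model is linear with a random intercept and time slope and complete data; SEs come from generalized least squares. The intercept SD is 1.5 throughout.

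| Slope SD; intercept-slope correlation; residual SD | Baseline to 12-month correlation | Mean post-baseline difference: SE ignoring → using baseline | 12-month difference: SE with arms free → equal at baseline | Treatment-by-time slope: SE with arms free → equal at baseline |
|---|---|---|---|---|
| 2.5; 0; 1.5 | 0.32 | 0.2368 → 0.2030 (14%) | 0.3468 → 0.3188 (8%) | 0.3239 → 0.3188 (2%) |
| 1.5; −0.3; 1 | 0.43 | 0.1727 → 0.1238 (28%) | 0.2124 → 0.1840 (13%) | 0.1991 → 0.1840 (8%) |
| 1.5; 0; 1 | 0.53 | 0.1986 → 0.1372 (31%) | 0.2510 → 0.1973 (21%) | 0.1991 → 0.1973 (1%) |
| 0.7; 0; 0.7 | 0.76 | 0.1794 → 0.0878 (51%) | 0.1948 → 0.1055 (46%) | 0.1064 → 0.1055 (1%) |

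Percentages are 1 − (second SE / first SE). In the last two columns baseline is one of the repeated responses.

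With post-baseline responses only, the slope SE with versus without the baseline covariate is unchanged in three scenarios and falls from 0.2052 to 0.2006 (2%) in the other. The 12-month SE in that setting falls by 6% (0.3475 to 0.3254) to 40% (0.1951 to 0.1166).

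**The case against.** The strongest reply is that the sentence is loose, not wrong. It glosses the random effects as random slopes or latent growth curves, promises overall as well as individual trajectories, and reads the variance of the random effects as heterogeneity. In a growth-curve model each random coefficient varies around a fixed mean, so fixed time, treatment and interaction terms may be implied. This stands. A reader might infer that the trial will have no treatment contrast for symptoms; the documents do not support that. They show that the contrast is not written down.

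A reader might also infer that baseline is discarded and precision lost. The text does not settle this. The instrument is scheduled at Visit 1 and continues from there, so baseline may already be a repeated response. A chance baseline difference is then absorbed by the treatment main effect, and the treatment-by-time term measures divergence from it. Step 3 shows little to gain for that slope. The single-follow-up rule, variance factor 1 − r², gives reductions of 9%, 25% and 49% at assumed r of 0.3, 0.5 and 0.7. Its comparator uses one post-baseline score, which is not the planned 4-weekly mixed model, so these are not losses under the plan.

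Section 9.3.2.1 does bring in demographics and treatment history, and Section 5.0 does provide for stratified analysis. Neither gives the baseline score a role, and neither is carried into Section 11.3.

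**Conclusion.** The point holds as a specification gap in a secondary analysis. That no fixed effects, contrast or role for baseline are stated is a matter of reading Section 11.3. That the literal random treatment terms are not identifiable, and do not estimate the lacosamide-placebo difference, follows from treatment being constant within a patient and needs no numerical assumption.

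The precision argument is conditional. Using baseline may materially reduce the SE of average or 12-month differences, by about 8% to 51% in the tabulated comparisons, with the covariate version at 12 months starting slightly lower at 6%. It changes the slope SE by only about 0% to 8%. These figures rest on assumed SDs and correlations, linear trajectories and complete data. The plan does not say which contrast it will report, so the actual loss, if any, cannot be computed.

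It would also go too far to say that this analysis decides the benefit-harm question: Section 9.3 calls it important to determine, but no decision rule depends on it.

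**What to change.** Rewrite the model sentence in Section 11.3 to state:

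- fixed effects for time, treatment and treatment-by-time;
- random effects limited to a patient intercept and a patient time slope;
- baseline MDASI-BT either as a covariate, with post-baseline scores as responses, or as a response with a common baseline mean across arms;
- adjustment for peri-operative AED use, the Section 5.0 factor that also stratifies the primary test;
- the contrasts to be reported: the fixed treatment and treatment-by-time effects, and which of the slope, average or 12-month difference is the main one.

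With a common baseline mean, the treatment difference at baseline is zero by construction, so later differences come from the treatment-by-time term. The model for binary symptom measures needs the same list.

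The cost is wording; the data are already being collected. There is one small downside: the covariate version drops patients without a baseline score and those with only a baseline score, which sits poorly with Section 11.3's aim of excluding no one. The common-mean version keeps them.
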